### 6.2 Secondary Endpoints

The secondary endpoint for SB subjects is change in bladder wall compliance as assessed by urodynamic studies (UDS) at study entry and study end.

We expect that SB subjects who perform CIC as prescribed will experience either no change or improvement in bladder compliance compared with those who do not improve their CIC adherence behavior. We expect nonadherence with CIC to result in either no change or worsening from baseline.

For KT subjects, the secondary endpoint is change in CV of immunosuppressive drug levels (tacrolimus or sirolimus) between the baseline (run-in) and intervention period. CV of immunosuppressive drug levels will be compared with the real-time adherence measures of mobile phone camera reporting.

Other important outcomes examined in exploratory analysis include rejection, de novo donor specific antibody accumulation, graft loss and death.

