### **3.1.2 Run-In and Intervention Phase**

During the first two weeks (run-in period) after questionnaire completion, all participants will be asked to take a photo of their medicines or catheter in hand at the time of treatment without prompts from Way to Health. The photo will be automatically transmitted to WTH and time stamped to record treatment adherence. Coordinators will emphasize that these data will be used to collect baseline information on the routine adherence behavior of AYA with KT and SB, and these data will not be reported to healthcare providers. Participants will receive \$20 (to be administered via Greenfire Clin Card), given as a lump sum at the end of the 2-week period. Participants can track payments in the WTH portal.

After the run-in period, coordinators will call participants to explain the randomization process. Participants will be told that WTH will randomly assign them to one of two groups and will notify them of their status by text. Participants will either be assigned to 1) access personal weekly adherence reports by logging into the WTH website or 2) receive weekly adherence reports automatically to their smartphone with direct feedback on their performance. Participants will also be told that they will receive ongoing weekly compensation for adherence reporting, but that the compensation structure will change and vary by group during the intervention so that we can learn more about the role of financial incentives for AYA.

**Study Arms:** At 2 weeks, a computerized randomization scheme will be generated by WTH to assign participants to one of two arms, stratified by disease group (KT or SB), and age category (12-17 vs. 18-24). User written code in Stata 14.0 will utilize a block randomization scheme that, within each disease/age group stratum stratification, first randomly orders blocks of size 2 and 4 and then randomly orders subjects within blocks. Due to the nature of the study, blinding of participants and research staff is not possible. However, the relying site PI's will

---

---

be blinded. WTH will send a text to each participant explaining the compensation scheme. Participants will be asked to reply yes to confirm receipt and willingness to participate. Additionally, coordinators will call participants at the time to explain the intervention and answer any questions. Subjects will be randomized as follows:

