### **3.3 Study Duration, Enrollment and Number of Sites**

#### **3.3.1 Duration of Study Participation**

The study duration per subject will be 12.5 months, with a 2-week run-in, 6-month intervention and 6-month follow-up.

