## **5 STUDY EVALUATIONS AND MEASUREMENTS**

### **5.1 Screening and Monitoring Evaluations and Measurements**

#### **5.1.1 Medical Record Review**

- Date of birth
  - Weight and height
  - Demographic data including age, race, gender, education level, insurance status, household income, possession of a 504/IEP plan, languages spoken at home, living arrangement and accessibility to care
  - Medical history, including reason for transplant, time since transplant, etiology of renal or hepatic disease, age at initial diagnosis, history and length of preceding dialysis, baseline GFR, transplant complications, and delayed graft function
  - Chart review in EPIC will be updated every 6 months from study entry for each
-

---

subject. For kidney transplant recipients, chart review will include immunosuppressive drug levels, hospitalization events, rejection episodes, graft failure events, biopsies and serum creatinine, number of medications, number of pills and other clinically relevant data. For spina bifida subjects, chart review will include level of lesion, type of spina bifida, number of shunt surgeries, ambulation method, other co-morbidities, baseline bladder capacity and compliance, route of catheterization, history of urinary tract infection, number of medications, frequency of catheterization and other clinically relevant data.

- No biopsies or any other medical procedures beyond standard of care will be done solely for this study. Study staff will review clinical biopsy results when chart reviews are completed.

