#### 6.5 Statistical Methods

Clinical and demographic variables will be compared with chi-square or two-sample t-tests for parametric and Fisher's exact or Wilcoxon rank-sum tests for non-parametric data. Treatment groups will be compared with similar analyses to confirm equity in randomization. We will compare change over time in % adherence between arms by fitting quasi-least squares (QLS) and generalized estimating equation (GEE) longitudinal models. The QLS/GEE models include a regression model for the primary outcome variable, in addition to a separate model for the correlation amongst the repeated measures on each subject. The AR (1) correlation structure is plausible because it forces a decline between measures with increasing separation in time; however, we will assess the sensitivity of results to choice of structure. In addition, the models will include treatment group and a time by treatment group interaction. If the interaction term differs significantly from zero, this will indicate that the change over time differs significantly between treatment groups. All analyses will follow the intention-to-treat principle. We will analyze the results for each disease group (SB, KT) separately, although the overall analytical models are the same.

Analysis for Aim 1 and Aim 2 will utilize GEE/QLS models to compare the change over time in the outcome between arms.

For Aim 3, Pearson's or Spearman's Correlations will be calculated to observe the association between outcome and each independent variable.

The statistical analysis will follow the intention-to-treat principle.

---

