## 3) EPIC Medical Record Data:

Study staff will extract relevant data (see section 5.1.1 Medical Record Review) from EPIC into REDCap via individual chart review. Individual subject data will be labeled with the subject's study ID upon population of REDCap for subsequent storage and data analysis.

Medical Record Review data will be managed and stored using the research-focused electronic web-based data capture system REDCap.

- Data listed in section 5.1.1 will be entered directly into REDCap. For exact data, please see the attached Medical Record Review survey (section 12.02 of our application)
  - Research staff from relying sites will be on-boarded as external collaborators under the umbrella of Data Access Groups. These coordinators will only have access to their site's participant data. Research staff from the DCC will have access to all sites' data.
  - Research staff at all sites will be required to obtain a Medical Authorization form to release/obtain patient information from the local institution to obtain medical record data of participant's transitioning to another institution for medical care during the study period. Method of receiving medical records data for participant's that consent to release of information will be determined by the institution's policy for sharing data.
-

- 
- The following de-identification options will be used, when necessary, when exporting data for analysis: removing known identifier fields, hashing of record names, removing invalidated Text fields, Notes fields, or date fields and date shifting.

Data backup is performed nightly via a dedicated backup system. The backup environment is maintained by a dedicated staff using dedicated resources. Access to the backup environment is restricted to Research Information Systems staff.

Some medical record data will be stored in WTH as well. This data includes the participant's date of birth, address, email address and phone number.

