#### **8.4.2 Risk Assessment**

There are no greater than minimal risks to subjects of this study. This is a randomized phase II clinical trial that will use participant clinical data obtained as part of routine medical care. Subjects in this study will not receive any additional medical procedures, such as biopsies or

---

---

lab work, beyond standard of care. Clinical data will be captured from the medical record database. This database is password protected and privilege for access is limited.

Subjects may decline to answer any question on any survey for any reason.

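### The KT drug-level CV endpoint is a change from a 2-week run-in, but nothing visible secures the two routine levels a run-in CV needs, and subtracting so sparse a baseline usually costs precision

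*Combined protocol and SAP*

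**What the plan says.** Section 6.2 gives the KT secondary endpoint as "change in CV of immunosuppressive drug levels (tacrolimus or sirolimus) between the baseline (run-in) and intervention period". Section 2.1 lists the same outcome under the primary objective simply as CV of drug levels, without mentioning change.

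The baseline window is short. Section 3.1.2 describes it as "During the first two weeks (run-in period) after questionnaire completion", and Section 3.3.1 gives each participant a "2-week run-in, 6-month intervention and 6-month follow-up".

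The levels are not study samples. Section 5.1.1 says: "For kidney transplant recipients, chart review will include immunosuppressive drug levels, hospitalization events, rejection episodes". The review is updated every 6 months, and Section 8.4.2 rules out any additional "lab work, beyond standard of care. Clinical data will be captured from the medical record database". Section 3.4.1 requires KT participants to be more than 3 months post-transplant and sets no criterion on number or recency of levels.

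On analysis, Section 6.5 says "Analysis for Aim 1 and Aim 2 will utilize GEE/QLS models to compare the change over time in the outcome between arms" and that "the models will include treatment group and a time by treatment group interaction". It does not name the CV endpoint.

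Section 3.1.1 places a medical record review after consent. Section 8.2 defers the detail to a form that is not shown: "For exact data, please see the attached Medical Record Review survey".

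**The concern.** A CV cannot be computed from one value, and from two values it is very noisy. The endpoint subtracts a CV from a 14-day window from one taken over 6 months, yet no visible text schedules levels in the run-in, sets a minimum number per window, or says what happens when no CV can be calculated.

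Two things are at stake. Many or all KT participants may have no baseline CV as the endpoint is worded. Where a baseline exists, the subtraction may add more noise than it removes. This is the only drug-level outcome named for KT, and it does not depend on participants' own photos.

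**Working it through.** **The plan's own figure.** Section 6.6 gives no power for this endpoint. The nearest figure is more than 90% power for the primary outcome with 90 per arm, a difference of 8 and an SD of 16 (effect size 0.5). It reproduces: 0.918 by the normal approximation, 0.916 by the noncentral t. I use the same 90 per arm below, with alpha 0.05 taken as two-sided.

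**Inputs from the documents.** Run-in 14 days; intervention 6 months; 180 evaluable KT participants, 90 per arm; levels from routine care only.

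**Assumed inputs.** The documents give no draw frequency, mean CV, between-person SD of CV or correlation between periods. All of these are my assumptions.

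**Step 1. Who has a run-in CV?** With regular draws more than 14 days apart, two cannot fall in the window, so nobody has one. With evenly spaced weekly draws, everyone has two. For irregular draws I assume a Poisson process with mean m = 14 / interval, so that P(at least 2) = 1 − e^(−m)(1 + m).

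| Average interval | m | P(at least 2) | Of 180 |
|---|---|---|---|
| 7 days | 2.00 | 59% | 107 |
| 14 days | 1.00 | 26% | 48 |
| 30 days | 0.47 | 8% | 14 |

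**Step 2. When does subtraction lose precision?** Let B be the run-in CV and P the intervention-period CV. Var(P − B) = Var(P) + Var(B) − 2 Cov(B, P), which exceeds Var(P) when Cov(B, P) is below half of Var(B).

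Example: two run-in and six intervention levels, mean CV 30%, between-person SD 10 points, correlation of true CVs 0.7. Simulation gives SD(B) = 18.1, SD(P) = 12.9 and an observed correlation of 0.162. Cov = 0.162 × 18.1 × 12.9 = 37.8, against 18.1² / 2 = 163.8. The SD of change is √(166.4 + 327.6 − 75.7) = 20.5, against 12.9 for P alone. The variance ratio is 2.5.

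**Step 3. A case favourable to the plan.** Everyone has exactly two run-in levels, as with even weekly draws, and 26 levels in the intervention and look-back windows. Levels are log-normal within person; true CV is log-normal between persons with mean 30% and SD 10 points; the between-period correlation is 0.3 to 0.9 on the log scale.

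Detectable difference at 80% power = 2.80 × SD × √(2/90) = 0.417 × SD.

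| Analysis | SD (points) | Detectable difference (points) |
|---|---|---|
| Change from run-in | 18.3–20.2 | 7.6–8.5 |
| Intervention-period CV alone | 10.9 | 4.5–4.6 |
| Adjusted for 6-month look-back CV | 7.9–10.6 | 3.3–4.4 |

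The ends of the ranges move by up to 0.1 between simulation runs. The variance ratio of change to intervention CV alone is 2.8 to 3.4.

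**Step 4. Where the ordering turns.** I varied the between-person SD (5, 10, 15, 20, 25 points), the number of run-in levels (2 or 3) and the correlation (0.3 to 0.98), giving 50 scenarios with even weekly draws. Change matched or beat unadjusted intervention CV in 9. All had an SD of 15 or more, and all but one had a correlation of 0.9 or more. With three levels, SD 20 and correlation 0.9 to 0.98, change detects 7.0–7.4 against 8.0–8.1 for intervention CV alone, but adjusted CV detects 4.3–5.1. The look-back-adjusted analysis detected a smaller difference than change in all 50.

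**Step 5. Bias.** At true CVs of 20, 30 and 40%, a two-level sample CV averages 15.6, 22.8 and 29.4; with 26 levels it averages 19.7, 29.5 and 39.0. With no true change, CV therefore appears to worsen within each arm by 4.1, 6.7 and 9.6 points. If sampling is similar in the two arms, this largely cancels in the comparison between them.

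**The case against.** The strongest reply is that the baseline window may be settled in the record-review form, which is not shown. A review follows consent, so levels already charted before the run-in may be abstracted, and the run-in label could stand loosely for everything before the intervention. That is possible, and if so the data for the fix are already to hand. But Section 6.2 as worded still puts the baseline at the run-in, so using earlier levels means changing that wording.

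A second reply is that every draw frequency, CV and correlation here is assumed, and that scenario counts on a chosen grid are not evidence about this trial. This stands. The size is conditional. The gap between a 14-day window and unscheduled sampling is not. The advantage of the look-back is also partly built in: it compares a 26-level covariate with a 2- or 3-level subtraction and gives the look-back the same correlation with the intervention period. Levels soon after transplant may be less representative.

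A reader might infer more than the documents support:

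- *That Section 6.5 prescribes the treatment-by-time interaction for CV.* That section describes models for adherence. Applying them to CV is an inference from its listing under the primary objective. If they are applied, participants with only an intervention CV are kept, but the change contrast still carries the noise of the run-in CV.
- *That change is always the worse analysis.* It is not, as Step 4 shows.
- *That the arm comparison is biased, or the primary endpoint compromised.* Neither is shown. The comparison of CV with photo-reported adherence can also use intervention-period CV.
- *That precise detectable differences can be quoted for irregular draws.* I give none, because the number of levels per person would itself vary.

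**Conclusion.** The point holds as a cheap improvement to one KT secondary endpoint. On the text alone, the baseline is tied to 14 days in which no provision secures the two levels a CV requires, and Sections 2.1 and 6.2 word the outcome differently.

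The consequence depends on routine sampling. It runs from no participant with a run-in CV (regular draws more than 2 weeks apart), through 8% to 59% (assumed Poisson draws every 30 to 7 days), to everyone with a two-level CV (even weekly draws). In that last case, under the assumed 30% mean CV and 10-point between-person SD, the subtraction raises the detectable difference from about 4.5 to about 8 CV points. Wide between-person spread, mostly with correlation of 0.9 or more, can reverse the ordering against unadjusted intervention CV. It did not do so against the look-back-adjusted analysis in any scenario examined. What is lost is precision.

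**What to change.** In Section 6.2, define the KT endpoint as the CV of routine drug levels over the 6-month intervention period, which agrees with Section 2.1, and state a minimum number of levels (for example 2, with 3 as a sensitivity analysis). In Section 6.5, name the analysis: compare arms in a model of intervention-period CV, adjusted for a baseline CV from a longer pre-randomisation chart window (for example up to 6 months, shorter for recent transplants). Keep participants without a baseline CV by a missing-baseline indicator or imputation. Report the number of levels per window by arm.

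The cost is protocol wording and a few more chart-review fields, with no added blood sampling. There are two limits:

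- The look-back adds little if levels are sparse. With six levels per window, the SD falls only from about 13.0 to between 11.9 and 12.9 points.
- The minimum applies to the intervention window too. With Poisson draws averaging every 30, 60 or 90 days (m = 183 / interval), about 98%, 81% or 60% would have at least two levels in 6 months. The rest have no intervention CV under either definition.

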### 6.3 Tertiary Endpoints

The tertiary endpoint is to identify psychosocial correlates of adherence changes in AYA with KT and SB. We hypothesize that improved treatment adherence from baseline to intervention

---

---

end will be mediated by increases in self-efficacy and healthcare responsibility and declines in perceived barriers, but will not be related to knowledge gained. We also hypothesize that we will observe greater changes in self-efficacy in Arm 2 vs. Arm 1 because of the specifically targeted text messages that emphasize people's progress and ability to perform difficult behavior. For this Aim, all participants will complete the baseline survey measures of self-efficacy, healthcare responsibility, perceived barriers and knowledge again at the end of the 6-month intervention via WTH. The **independent variables** in the analyses for Aim 3 are: 1) change in self-efficacy score 2) change in healthcare responsibility score 3) change in perceived barriers and 4) change in knowledge score from baseline to end of intervention. The **dependent variable**, or primary outcome measure, is: change in the *proportion of weeks with adherence behavior performance  $\geq 85\%$  prescribed/expected between baseline (run-in period) and intervention period*. A secondary analysis will examine usage of the educational modules viewed in the WTH portal. Usage will be tracked as yes/no and time spent. We hypothesize that increased usage will associate with increased knowledge but will have no effect on increased treatment adherence. Prior research supports the hypothesis that increased knowledge is not sufficient to promote positive health behavior.

#### 6.4 Quaternary Endpoints

The quaternary objective is to evaluate differences in comorbidities and demographic data of lost to follow up participants to that of those who are complete the study intervention. We hypothesize participants with comorbid or more severe conditions may be less likely to complete or participate in the study.

#### 6.5 Statistical Methods

Clinical and demographic variables will be compared with chi-square or two-sample t-tests for parametric and Fisher's exact or Wilcoxon rank-sum tests for non-parametric data. Treatment groups will be compared with similar analyses to confirm equity in randomization. We will compare change over time in % adherence between arms by fitting quasi-least squares (QLS) and generalized estimating equation (GEE) longitudinal models. The QLS/GEE models include a regression model for the primary outcome variable, in addition to a separate model for the correlation amongst the repeated measures on each subject. The AR (1) correlation structure is plausible because it forces a decline between measures with increasing separation in time; however, we will assess the sensitivity of results to choice of structure. In addition, the models will include treatment group and a time by treatment group interaction. If the interaction term differs significantly from zero, this will indicate that the change over time differs significantly between treatment groups. All analyses will follow the intention-to-treat principle. We will analyze the results for each disease group (SB, KT) separately, although the overall analytical models are the same.

Analysis for Aim 1 and Aim 2 will utilize GEE/QLS models to compare the change over time in the outcome between arms.

For Aim 3, Pearson's or Spearman's Correlations will be calculated to observe the association between outcome and each independent variable.

The statistical analysis will follow the intention-to-treat principle.

---

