## **2.2 Secondary Objective**

The secondary objective is to evaluate differences in sustainability of adherence in a 6-month post-intervention period in which financial incentives are tapered then stopped in Arm 2. We will compare the change in adherence from the intervention's end to 6 months post-intervention. Hypothesis 2: Arm 2 (vs. Arm 1) will demonstrate greater sustained adherence as incentives are slowly removed due to ongoing tailored feedback.

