### **3.4.2 Exclusion Criteria**

- 1) Unwilling to participate.
- 2) Unable to speak or read in English.
- 3) Unable to provide informed assent or consent.
- 4) Severe cognitive impairment, as reported by treating team in recruiting clinic.
- 5) On dialysis
- 6) Acquired post-transplant lymphoproliferative disease less than one year prior to enrollment
- 7) Less than 3 months post-transplant.
- 8) Unable to perform CIC.
- 9) Prescribed Immunosuppressive medications once per day.
- 10) Provider recommendations of CIC once per day

Parents/legal guardians meet the inclusion criteria if their child is eligible for the study. Parents/legal guardians will be excluded if they meet one or more of items #1-4 of the above exclusion criteria. Subjects that do not meet all of the enrollment criteria may not be enrolled. If a subject's parent is unwilling to participate, the subject may still enroll in the study. In this case, clinical information about the parent, such as household income and education level, will not be collected. Any violations of these criteria must be reported in accordance with IRB Policies and Procedures.

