## 6 STATISTICAL CONSIDERATIONS

### 6.1 Primary Endpoint

The primary endpoint for this pilot clinical trial is to compare the efficacy of two 6-month mhealth-based interventions to promote treatment adherence among AYA with KT or SB.

The **independent variable** in the analyses for Aim 1 is *exposure to feedback + incentive* (intervention, Arm 2). The **dependent variable**, or primary outcome measure, is: change in the *proportion of weeks with adherence behavior  $\geq 85\%$  expected between baseline (run-in period) and intervention period*. Weekly adherence proportions will be calculated by observing the number of non-missed/late treatment episodes over the total number of episodes in that week.

The outcome will then be the proportion of weeks with treatment adherence  $\geq 85\%$ . Participants who do not submit the correct number of pictures within the prescribed window of their expected time due for treatment will be counted as nonadherent for that episode of med taking/cathing. Over the study period, changes in weekly timing adherence will be assessed as a repeated measure over time. In secondary analysis, we will examine variability in inter-dose intervals (based on time-stamping of photos) to account for doses that are taken beyond the time window.

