## 6.6 Sample Size and Power

The disease groups (KT or SB) will be analyzed separately in the primary analysis. We assume 180 KT and 180 SB recipients will complete the study, allowing for 10% drop-outs. With 90 participants per arm per disease group, setting alpha at 0.05, we will have >90% power to detect a medium effect size of 0.5 in timing change in proportion of timing adherence, using a two group t-test (based on TAKE-IT). Based on preliminary data from TAKE IT and published studies, it is reasonable to expect an average of 8% improvement in timing adherence when a behavioral economics model with financial incentives is applied. An effect size of 0.50 would be observed if the difference in average improvement was 8% between groups, while the standard deviation of post minus pre improvement was 16. With 90 subjects per arm, the detectable effect size is also 0.50 for Aim 2. For Aim 3, a 0.050 two-sided Fisher's z test of the null hypothesis that the Pearson correlation coefficient is 0 will have 82% power to detect a correlation of 0.300 when the sample size is 90.

Table 3. Anticipated Participant Enrollment				
	Year 1	Year2	Year 3	Year 4 *
Expected Participant Recruitment (Cohort 1 and 2)	100	100	100	100
Expected Parent Recruitment (Cohort 3)	200	200	200	200
Anticipated drop-outs (10%)	30	30	30	30
Anticipated cumulative n by end of study year	270	540	810	1080

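### Aim 1 subtracts a two-week pre-randomisation run-in instead of adjusting for it; section 6.5 names neither run-in adherence nor age category as a covariate, which gives up precision but not validity

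*Combined protocol and SAP*

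**What the plan says.** Everyone completes a two-week run-in of unprompted photo reporting, and assignment follows (section 3.1.2): "At 2 weeks, a computerized randomization scheme will be generated by WTH to assign participants to one of two arms". Randomisation is stratified by disease group and by age category, 12-17 against 18-24 (sections 3.1.2, 3.2, 8.1.1).

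Section 6.1 scores each week by the fraction of treatment episodes neither missed nor late, and marks whether that reaches 85%. "The outcome will then be the proportion of weeks with treatment adherence" at or above that level, and Aim 1 concerns its change from run-in to intervention.

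Section 6.5 fits GEE/QLS models, separately in KT and SB, with AR(1) as the favoured correlation. On that choice it adds: "we will assess the sensitivity of results to choice of structure". On the mean model it says: "In addition, the models will include treatment group and a time by treatment group interaction". The interaction is the test. No covariate is named, and neither the coding of time nor the link is stated.

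Section 6.6 bases power on a two-group t-test for "a medium effect size of 0.5 in timing change in proportion of timing adherence", with a difference of 8 and a standard deviation of change of 16.

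**The concern.** A baseline measured before randomisation has the same expectation in both arms. A change score does not use that fact. It subtracts each participant's run-in value with a coefficient of 1, however noisy the value is. Here it rests on two weeks, is reduced to 0, 0.5 or 1, and is taken from a proportion over about 26 weeks. Regression on the run-in value chooses the coefficient from the data, so in large samples it cannot be less precise than subtracting the value whole.

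Age category was thought important enough to stratify on. Because the disease groups are analysed separately, it is the only stratification factor left within each analysis, yet 6.5 does not name it.

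At stake is the width of the Aim 1 confidence interval in each disease group. The data that would narrow it are already collected.

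**Working it through.** **1. The plan's own figure.** Inputs from 6.6: 90 per arm, difference 8, SD of change 16, alpha 0.05 (two-sided assumed, since 6.6 does not say for Aim 1). Standardised effect 8/16 = 0.5; noncentrality 0.5 × √(90/2) = 3.354; 178 degrees of freedom. Power from the noncentral t is 91.6%, so the stated figure reproduces. It is for timing adherence under a t-test, not for the proportion of weeks at or above 85% under GEE/QLS, so no revised power is derived from it here.

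**2. Same target.** Let P be the run-in value and Y the intervention-period value. The arm difference in E(Y − P) equals the arm difference in E(Y), because E(P) is common to the arms. On the identity scale, adjustment leaves the estimated quantity unchanged.

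**3. Change against adjustment.** Per-subject variances:
- change: Var(Y) + Var(P) − 2Cov(P,Y)
- adjusted: Var(Y) − Cov(P,Y)²/Var(P)

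The correlations are assumptions. P is the mean of 2 weeks and Y the mean of 26 (6 months), each week with variance 1. Example, exchangeable 0.3: Var(P) = 1.3/2 = 0.65; Var(Y) = (1 + 25 × 0.3)/26 = 0.327; Cov = 0.3. Change = 0.327 + 0.65 − 0.6 = 0.377. Adjusted = 0.327 − 0.09/0.65 = 0.188. Ratio 2.00.

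| Assumed weekly correlation | Change | Adjusted | Ratio |
|---|---|---|---|
| AR(1) 0.80 | 0.911 | 0.266 | 3.43 |
| AR(1) 0.90 | 0.817 | 0.382 | 2.14 |
| AR(1) 0.95 | 0.598 | 0.390 | 1.53 |
| Exchangeable 0.3 | 0.377 | 0.188 | 2.00 |
| Exchangeable 0.7 | 0.162 | 0.135 | 1.20 |
| Exchangeable 0.9 | 0.054 | 0.051 | 1.05 |

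With a persistent subject effect (share 0.3 to 0.7) plus AR(1) (0.3 to 0.8), the ratio is 1.24 to 2.22. Interval width scales with 1/√ratio: about 2% narrower at 1.05 and 46% narrower at 3.43.

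**4. The dichotomised outcome.** Sixteen simulated scenarios used 14 or 28 episodes a week. The lower figure is two a day, since 3.4.2 excludes participants "Prescribed Immunosuppressive medications once per day". Change variance over adjusted variance was 1.22 to 4.42 with run-in share as covariate and 1.44 to 4.56 with share plus the continuous run-in percentage. With the percentage alone it was 0.80 to 4.56, below 1 in two scenarios. All scenario parameters are assumed.

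**5. Age category.** Placed beside run-in in the adjusted analysis, with age explaining 2% to 10% of weekly variance, it gives a further ratio of 1.00 to 1.15 in most cases, and up to 1.27 at AR(1) 0.80. Added only as a main effect to the interaction model it does nothing: in 150 simulated fits the interaction estimate was identical with no covariate, with age, and with age plus run-in.

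**6. Against the AR(1) interaction itself.** With step-coded time and AR(1) 0.90, that contrast puts 92% of its intervention weight on the first intervention week. Its per-subject variance is 0.193, against 0.382 for the adjusted 26-week mean. The ratio of interaction variance to adjusted variance is 1.35, 0.51 and 0.25 at AR(1) 0.80, 0.90 and 0.95, and 0.52 to 2.21 with a subject effect plus AR(1).

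**7. Common run-in mean as an alternative.** Take AR(1) as working correlation, a true structure of subject effect plus AR(1) as in step 3, and sandwich variance. The variance with a free run-in mean per arm over that with a common mean is 0.88 to 1.62 for step time. For linear weekly time it is 0.24 to 1.41, below 1 in 8 of 9 settings. Values below 1 mean that the constraint loses precision.

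**The case against.** The strongest reply is that this is preference, not error. The endpoint is a change, the test is of change, power was computed for change, and every ratio above rests on assumed correlations. That stands as far as it goes: the plan is valid and the size of the gain cannot be fixed from the documents. It does not remove the point, because adjustment keeps the target (step 2) and can only help, in large samples, against the change outcome that 6.1 defines.

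A second reply is that 6.5 plans a GEE/QLS interaction, not a raw change score, so the gain over the actual model is not shown. That also stands. Step 6 shows the adjusted analysis can have the larger variance. The comparison is not like for like, because the AR(1) step contrast mainly compares the weeks next to randomisation, while 6.1 asks about the whole intervention period.

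A reader might also infer that keeping run-in weeks as responses with a common mean is a safe gain. It helps when the covariance is unstructured or correctly specified. Section 6.5 favours AR(1), which cannot represent a stable difference between adherent and non-adherent participants, and step 7 shows the constraint can then raise the variance.

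**Conclusion.** The point holds as a matter of precision. Against the change in the 26-week outcome, adjusting for run-in lowers the variance by a factor of about 1.05 to 3.4 under the assumed correlations. The gain is near nil when run-in and intervention are almost perfectly correlated. Age category adds little.

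A reader might go further and conclude that Aim 1 is biased or underpowered, or that adjustment would lift the 91.6% to some higher figure. The documents do not support either. Randomisation protects the change comparison, the stated power reproduces on its own scale, and no run-in SD, intervention SD or correlation is given from which to compute power for the 6.1 outcome. Nor do they support a claim that the adjusted analysis beats every form of the planned interaction model.

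Aim 2 is outside the point. Section 2.2 says: "We will compare the change in adherence from the intervention's end to 6 months post-intervention". Its starting level is measured after randomisation, so the argument from a shared baseline does not apply.

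**What to change.** In 6.5, for each disease group, state that the Aim 1 estimate is the arm difference in the intervention-period proportion of weeks at or above 85%, adjusted for:
- the run-in share of weeks at or above 85%, with the continuous run-in percentage optionally beside it but not in its place;
- randomisation age category (12-17 against 18-24).

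State the link; with a logit link, standardise to the marginal difference between arms. If the longitudinal interaction model is kept as a supporting analysis, state how time is coded. Do not rely on adding age or run-in as main effects to that model, and do not make a common run-in mean the default under an AR(1) working correlation. Leave Aim 2 as it is.

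The cost is a few sentences and two or three degrees of freedom out of about 180 per disease group, plus a standardisation step if a logit link is used. No new data are needed.
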